The proportions of responders at selected timepoints in total NPS and SNOT-22 total score will be analysed using logistic regression with treatment arm, baseline scores of corresponding endpoint, region, and baseline CCI status CCI) as covariates.

The proportion of patients who had CRSwNP surgery, the proportion of patients who had SCS for CRSwNP, and the proportion of patients who had CRSwNP surgery and/or SCS for CRSwNP up to Week 56 will be analysed using a Cochran–Mantel–Haenszel test controlling for region, and baseline CCI status CCI).

Analyses of pharmacokinetic variables

Benralizumab serum concentrations will be summarized using descriptive statistics. The population PK analysis will be presented separately from the main CSR.

Analyses of immunogenicity variables

Anti-drug antibodies status and the titers will be summarized using descriptive statistics. The impact of ADA on PK and eosinophil level will be assessed. The potential association of ADA with safety and efficacy will also be evaluated.

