2.1.4 Pharmacokinetic analysis set

All patients who received benralizumab and from whom PK blood samples are assumed not to be affected by factors such as protocol deviations and who had at least one measurable serum PK observation post first dose will be included in the PK analysis dataset.

Pharmacokinetic analyses will be conducted based on the PK analysis set.

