4.2.8.1 Analysis of pharmacokinetic variables

Benralizumab serum concentrations will be summarised by using descriptive statistics during the DB period using the PK analysis set, and during the OLE period using the OLE analysis set. In addition, geometric mean, coefficient of variation (CV), lower (Q1), and upper (Q3) quartiles will also be reported.

Serum concentrations, that are below the LLOQ (<LLOQ) or if there are missing values, will be handled as follows:

- All values <LLOQ will be set to LLOQ/2. Missing values will be set to “NA”.
- At a time point where mean is <LLOQ, Not Applicable (N/A) will be written in the field for SD, CV%, and 95% CI. The maximum value will be reported from individual data. If median is <LLOQ then shall be reported as <LLOQ, otherwise reported from individual data. The minimum value will be reported as <LLOQ.
- If all values are <LLOQ at a time point, no descriptive statistics will be calculated for that time point. Not Applicable (N/A) will be written in the field for SD, CV%, and 95% CI, and <LLOQ will be written in fields for the mean, geometric mean, minimum, median and maximum.

The LLOQ of Benralizumab in serum will be 3.86 ng/mL.

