ADA response (positive or negative) and titre will be summarised at baseline and at all scheduled post-baseline visits by treatment group using derived visit windows (refer to Section 3.1.2 for detailed definition of visit windows) in each study period. In the event a patient has more than one result within a given visit window, the maximum ADA titre will be used in the by-visit summary. In addition, the ADA response will be presented cumulatively. The cumulative ADA response is positive for a specific visit if a positive ADA result is detected at any time point up to and including the specific visit. If all ADA result are negative up to the specific visit, then the cumulative ADA response is negative for that visit. A summary of the number and percentage of patients who are ADA positive at a post-baseline assessment for the first time by visit will also be presented. A line plot of serum concentrations over time will be provided by ADA categories.

The proportion of patients with positive nAb response will be summarised by visit. Key patient information will be listed for patients with positive ADA results, including ADA status, nAb status, titer, benralizumab serum concentration, and blood eosinophil level.

All analyses will be conducted by treatment group on the safety analysis set for the DB period and the on-study period, and on the OLE analysis set for the OLE period, unless otherwise specified. All ADA results will be listed. Results from the DB period will be reported at the primary DBL while remaining results from OLE period and the on-study period will be reported at the final DBL.

ADA and blood eosinophil levels

Eosinophil levels will be summarised by visit and for the following ADA response categories of patients:

For the DB period: ADA negative, ADA positive, treatment-emergent ADA positive, non-treatment-emergent ADA positive, ADA persistently positive, ADA transiently positive, nAb-positive, and treatment-emergent ADA positive with maximum post-baseline titer > median of maximum post-baseline titre.

For the OLE period: ADA negative, ADA positive, newly treatment-emergent ADA positive, non-treatment-emergent ADA positive, newly ADA persistently positive, stable ADA persistently positive, nAb-positive, ADA transiently positive, and treatment-emergent ADA positive with maximum post-baseline titer > median of maximum post-baseline titre.

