For the on-study period: ADA negative, ADA positive, treatment-emergent ADA positive, non-treatment-emergent ADA positive, ADA persistently positive, ADA 6-month persistently positive, ADA 12-month persistently positive, ADA transiently positive, treatment-emergent

ADA positive with maximum post-baseline titer > median of maximum post-baseline titre and nAb-positive.

A line plot of blood eosinophil levels by visit and ADA status will also be presented.

ADA and efficacy

The effects of ADA on the co-primary endpoints calculated during the DB period will be evaluated through summary statistics by treatment group and ADA status (i.e. ADA negative, ADA positive, treatment-emergent ADA positive, non-treatment-emergent ADA positive, ADA persistently positive, ADA transiently positive, nAb-positive, and treatment-emergent ADA positive with maximum post-baseline titer > median of maximum post-baseline titre). Due to the expected small number of ADA positive patients in the placebo group, no formal statistical comparisons of benralizumab versus placebo by ADA status (positive/negative) are planned.

ADA and safety

Adverse events during the DB period and the OLE period will be summarised by treatment group and ADA status (i.e. ADA negative, (newly) TE-ADA positive, and non-TE-ADA positive) over safety analysis set and OLE analysis set, respectively. The potential impact of ADA on hypersensitivity will also be assessed.

ADA and PK

Similarly as blood eosinophil levels, benralizumab serum concentrations will be summarised by treatment group, visit and ADA status for patients in the PK analysis set for the DB period, OLE period, as well as on-study period.

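### The SAP 8.7 table of drug level by ADA status leaves out treated patients with no measurable post-dose concentration, and so may understate an ADA-related loss of exposure

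*SAP*

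**What the plan says.** Protocol 9.4.1.2, under immunogenicity, states the aim: "The impact of ADA on PK and eosinophil level will be assessed". SAP 8.7 (ADA and PK) carries it out with one table, for the double-blind, open-label and on-study periods: "benralizumab serum concentrations will be summarised by treatment group, visit and ADA status for patients in the PK analysis set".

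SAP 2.1.4 limits that set. Of the patients who received benralizumab and whose samples are assumed unaffected by protocol deviations, only those "who had at least one measurable serum PK observation post first dose will be included in the PK analysis dataset". Protocol 9.3 has the same condition. SAP 2.1.4 adds a general rule: "Pharmacokinetic analyses will be conducted based on the PK analysis set".

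Other parts of the SAP bear on the point:

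- SAP 4.2.8.1 keeps single values below the limit: "All values <LLOQ will be set to LLOQ/2". The LLOQ is 3.86 ng/mL.
- The default set in SAP 8.7 is different: "All analyses will be conducted by treatment group on the safety analysis set for the DB period and the on-study period", with the OLE analysis set for the open-label period, unless otherwise specified.
- SAP 8.7 plans two further outputs with concentrations and names no set for either: "A line plot of serum concentrations over time will be provided by ADA categories", and "Key patient information will be listed for patients with positive ADA results, including ADA status, nAb status, titer, benralizumab serum concentration".
- The subgroup analysis by PK quartile in SAP 4.2.5.3 asks only that a post-baseline sample was collected, not that it was measurable.

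**The concern.** Entry to the table depends on the quantity that the table describes. The most extreme effect an antibody could have on exposure is to leave no measurable drug at any visit, and a patient in that state is removed before the summary is made. Partial loss can show in this table. Complete loss cannot.

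The same patient stays in the ADA counts and in the eosinophil summary by ADA status, which fall under the safety-set default for the double-blind and on-study periods. The paired PK and eosinophil tables can therefore rest on different patients. Someone who lost drug and regained eosinophils could appear in one and not in the other. At stake is whether a reader of the report can take the table at face value as the answer to the protocol's stated aim.

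**Working it through.** The documents give no figure to reproduce here, so the check has three parts.

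**1. Can a treated patient be excluded?** In the Schedule of Activities (protocol Table 2), double-blind PK samples after Week 0 fall at Weeks 16, 24, 40 and 56, and samples at dosing visits are taken pre-dose. Week 16 is eight weeks after the third dose (Week 8). Apart from an early discontinuation visit or an extra agreed sample, nothing earlier could qualify a patient whose exposure is lost before Week 16. Exclusion needs every post-dose sample to be unmeasurable. One measurable value keeps the patient in, with the other values at 3.86/2 = 1.93 ng/mL. The SAP does not define measurable; I read it as at or above LLOQ.

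**2. Direction and size.** Assumed, because the documents give none of these:

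- f: share of ADA-positive patients below LLOQ throughout
- r: geometric mean ratio, ADA-positive to ADA-negative, among patients with a measurable value
- G: ADA-negative geometric mean trough, with no ADA-negative patient excluded

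The table as planned shows r. With everyone kept, the ratio is exp[(1−f) ln r + f ln(1.93/G)].

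Example with r = 0.5, f = 0.10, G = 100: 0.9 × (−0.693) + 0.1 × (−3.948) = −1.019, which gives 0.361. With G = 1000: −0.624 − 0.625 = −1.249, which gives 0.287.

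| f | r = 0.5, G = 100 to 1000 | r = 1.0, G = 100 to 1000 |
|---|---|---|
| 0 | 0.50 | 1.00 |
| 5% | 0.425 to 0.379 | 0.821 to 0.732 |
| 10% | 0.361 to 0.287 | 0.674 to 0.535 |
| 25% | 0.222 to 0.125 | 0.373 to 0.210 |

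The choice of statistic matters. Suppose 15 ADA-positive patients, k of them below LLOQ throughout and the rest at T = 100 or 200 ng/mL. The planned table reports T. With all 15 kept, the geometric mean is exp[((15−k) ln T + k ln 1.93)/15] and the arithmetic mean is ((15−k)T + 1.93k)/15.

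| k | Geometric mean, all 15 (T = 100; 200) | Reported/all | Arithmetic mean: reported/all |
|---|---|---|---|
| 2 | 59; 108 | 1.7 to 1.9 | about 1.15 |
| 3 | 45; 79 | 2.2 to 2.5 | about 1.25 |
| 5 | 27; 43 | 3.7 to 4.7 | about 1.49 |

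The median of all 15 is still T for each of these k. SAP 4.2.8.1 plans the geometric mean as well as the mean and median.

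**3. How many patients?** Take about 125 on benralizumab (250 randomised 1:1), an assumed ADA rate a of 5% to 20%, and f of 5% to 25%. The expected number excluded is 125 × a × f, from 125 × 0.05 × 0.05 = 0.3 to 125 × 0.20 × 0.25 = 6.2. The chance of at least one is 1 − (1 − af)^125, from 27% to almost 100%.

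**The case against.** The strongest reply is that this is one descriptive table among several outputs. That stands in part. The listing in SAP 8.7 is tied to a positive ADA result and shows titre, nAb status, concentration and eosinophils together, so an ADA-positive patient below LLOQ throughout should appear there. The line plot arguably falls under the safety-set default too, although the general rule in SAP 2.1.4 points to the PK analysis set, so its population is unclear. A reader might infer that ADA and drug level are examined only in patients with measurable drug, or that a test of ADA on PK is biased. The documents support neither: these other outputs exist, and no such test is planned. Nor does the condition reach every PK summary, because SAP 4.2.8.1 puts open-label concentrations on the OLE analysis set.

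The exclusion is also narrow. A patient who completes the double-blind period has four scheduled chances to give a measurable value, so intermittent or late loss is captured.

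The direction is conditional. A patient who stopped study drug early but stayed in follow-up could be below LLOQ for reasons unrelated to ADA. If ADA-negative, that patient's exclusion works the other way. Nothing in the documents shows that exclusions would gather in the nAb-positive, persistent or high-titre groups.

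What does not stand is that the listing makes up for the table. A line listing does not correct a summary statistic, and a reader of the table is not told how many patients are missing from it or why.

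**Conclusion.** The point holds for the ADA-by-PK summary table. As planned, it cannot show complete loss of exposure. It understates the ADA-related fall if the patients left out are disproportionately ADA-positive. The effect is nil if no patient is below LLOQ throughout, modest on the arithmetic mean if a few are, and possibly large on the geometric mean, which is the statistic most sensitive to the 1.93 ng/mL substitution. The ADA rate, the troughs and the number below LLOQ are all assumptions, so the figures show a range and predict nothing. No efficacy conclusion, alpha allocation or formal test depends on this table. It is a cheap improvement to a descriptive safety and pharmacology output.

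**What to change.** In SAP 8.7 (ADA and PK):

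- Base the summary on all benralizumab-treated patients with at least one evaluable post-first-dose PK sample collected, measurable or not. This follows the collected-sample rule already used in SAP 4.2.5.3. Set values below LLOQ to LLOQ/2 as in 4.2.8.1.
- Report, by ADA category, the number of patients with all post-dose values below LLOQ.
- Name the same set for the line plot of concentrations by ADA category.
- Reconcile the set for open-label concentrations: the OLE analysis set in 4.2.8.1, the PK analysis set in 8.7.

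Leave the definition in SAP 2.1.4 alone. It matches protocol 9.3, and SAP Section 6 declares no changes from the protocol. Protocol 9.4.1.2 lists the impact of ADA on PK under immunogenicity, and protocol 9.3 places immunogenicity on the safety analysis set, so a wider set for this table fits the protocol. If the sponsor regards the table as a PK analysis, a line in Section 6 would cover it.

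The cost is a few sentences and no new data. Reported mean troughs by ADA status may be slightly lower.

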8.8 Worst possible scores

The worst possible scores as given in the table below for each endpoint will be used for analyses in which the WP imputation method is used after surgery for CRSwNP.

Table 13 Worst possible scores

Endpoint	Worst Possible Score
NPS	8
NBS/DSS/NPSD individual item	3
SNOT-22 total score	110
SNOT-22 individual item	5
LMS	24
Zinreich total score	54
Sinus severity score	100
TSS	24
UPSIT	0
ACQ-6	6
SF-36 components	
PCS	7.32

Endpoint	Worst Possible Score
MCS	5.79
PF	19.26
RP	21.23
BP	21.68
GH	18.95
VT	22.89
SF	17.23
RE	14.39
MH	11.63
PGI-S	5 (very severe)
PGI-C	7 (much worse)

8.9 Random seeds

The starting random seeds to be utilised in the MCMC and monotone regression MI are provided in the table below. For each successive visit imputed in the monotone regression MI (step 2 in Section 4.2.5.1), the random seed increments by 1. For example, imputation of Week 8 of NPS in monotone regression MI uses a seed of 288263, imputation of Week 16 of NPS uses 288264, and so on.

Table 14 Random seeds for multiple imputation analyses

Endpoint	Primary/CO VID MCMC	Primary /COVID MI	WP after Surgery MCMC	WP after Surgery MI	DRMI MCMC	DRMI MI
NPS	97348	288263	504986	438656	454805	536844
NBS (NPSD)	72766	714699	482798	804161	88386	459794
DSS (NPSD)	875052	519837	820852	680071	945412	172159
Nasal congestion (NPSD)	585248	518131	NA	NA	NA	NA
Runny nose (NPSD)	987759	285595	NA	NA	NA	NA
Postnasal drip (NPSD)	945217	86342	NA	NA	NA	NA
Headache (NPSD)	146002	930824	NA	NA	NA	NA
Facial pain (NPSD)	332834	604107	NA	NA	NA	NA
Facial pressure (NPSD)	280036	66016	NA	NA	NA	NA
Diff with sleeping (NPSD)	216628	431468	NA	NA	NA	NA
Diff with daily activities (NPSD)	483627	252059	NA	NA	NA	NA
TSS (NPSD)	135121	501498	NA	NA	NA	NA
SNOT-22	851498	608526	599733	263466	486856	513807
CT (LMS, SSS, ZS)	NA	NA	NA	NA	NA	NA
UPSIT	545559	925322	NA	NA	NA	NA
ACQ-6	655030	598573	NA	NA	NA	NA

8.10 Efficacy estimands

Statistical Category	Estimand ¹			SAP Section
	Endpoint (Population)	Intercurrent Event Strategy ¹	Population Level Summary ¹ (Analysis)	
Primary objective: To evaluate the effect of benralizumab on nasal polyp burden and patient-reported nasal blockage				
Co-Primary/MCP	
 CFB in endoscopic total NPS (severe CRSwNP patients with asthma) CFB in bi-weekly mean NBS (severe CRSwNP patients with asthma) 	Included in analysis regardless of treatment discontinuation; WP after surgery for CRSwNP, WOCF after SCS use for CRSwNP ³ (primary estimand)	Mean difference between interventions at Week 56 ² (LSMD from CFB ANCOVA following hybrid WP/WOCF and MI)	Section 4.2.5.1
Supplementary and Sensitivity	
 CFB in endoscopic total NPS (severe CRSwNP patients with asthma) CFB in bi-weekly mean NBS (severe CRSwNP patients with asthma) 	
 Included in analysis regardless of treatment discontinuation or SCS use for CRSwNP; WP after surgery for CRSwNP⁴ Disc of treatment assumed based on DRMI³ Remained adherent to treatment without surgery or SCS use for CRSwNP⁵ (effectiveness) Included in analysis regardless of treatment discontinuation; surgery or SCS use for CRSwNP⁶, (treatment policy) 	
 Mean difference between interventions at Week 56² (LSMD from CFB ANCOVA following hybrid WP and MI) Mean difference between interventions at Week 56² (LSMD from CFB ANCOVA following hybrid WP/WOCF and DRMI) Mean difference between interventions at Week 56² (LSMD from CFB repeated measures ANCOVA) Mean difference between interventions at Week 56² (LSMD from CFB repeated measures ANCOVA) 	Appendix 8.2 Appendix 8.3 Appendix 8.4 Appendix 8.5
Key Secondary Objective: To evaluate the effect of benralizumab on sense of smell				
Secondary/MCP	CFB in bi-weekly mean DSS (severe CRSwNP patients with asthma)	Included in analysis regardless of treatment discontinuation; WP after surgery for CRSwNP, WOCF after SCS use for CRSwNP ³ (primary estimand)	Mean difference between interventions at Week 56 ² (LSMD from CFB ANCOVA following hybrid WP/WOCF and MI)	Section 4.2.6.1

Statistical Category	Estimand ¹			SAP Section
	Endpoint (Population)	Intercurrent Event Strategy ¹	Population Level Summary ¹ (Analysis)	
Supplementary and Sensitivity	• CFB in bi-weekly mean DSS (severe CRSwNP patients with asthma)	
 • Included in analysis regardless of treatment discontinuation or SCS use for CRSwNP; WP after surgery for CRSwNP⁴ • Disc of treatment assumed based on DRMI³ • Remained adherent to treatment without surgery or SCS use for CRSwNP⁵ (effectiveness) • Included in analysis regardless of treatment discontinuation; surgery or SCS use for CRSwNP⁶, (treatment policy) 	• Mean difference between interventions at Week 56 ² (LSMD from CFB ANCOVA following hybrid WP and MI)	Appendix 8.2
			• Mean difference between interventions at Week 56 ² (LSMD from CFB ANCOVA following hybrid WP/WOCF and DRMI)	Appendix 8.3
			• Mean difference between interventions at Week 56 ² (LSMD from CFB repeated measures ANCOVA)	Appendix 8.4
			• Mean difference between interventions at Week 56 ² (LSMD from CFB repeated measures ANCOVA)	Appendix 8.5
Key Secondary Objective: To evaluate the effect of benralizumab on sinus opacification				
Secondary/MCP	CFB in mean LMS (severe CRSwNP patients with asthma)	Included in analysis regardless of treatment discontinuation or SCS use for CRSwNP; WP after surgery for CRSwNP ⁴ , (primary estimand)	Mean difference between interventions at EoDB/IPD (LSMD from CFB ANCOVA following WP at EoDB/IPD)	Section 4.2.6.2
Supplementary	CFB in mean LMS (severe CRSwNP patients with asthma)	Included in analysis regardless of treatment discontinuation; WP/WOCF after surgery ³ and SCS use for CRSwNP	Mean difference between interventions at EoDB/IPD (LSMD from CFB ANCOVA following WP/WOCF at EoDB/IPD)	Section 4.2.6.2
Key Secondary Objective: To evaluate the effect of benralizumab on disease specific health-related quality of life				
Secondary/MCP	CFB in mean SNOT-22 (severe CRSwNP patients with asthma)	Included in analysis regardless of treatment discontinuation; WP after surgery for CRSwNP, WOCF after SCS use for CRSwNP ³ (primary estimand)	Mean difference between interventions at Week 56 ² (LSMD from CFB ANCOVA following hybrid WP/WOCF and MI)	Section 4.2.6.3

Statistical Category	Estimand ¹			SAP Section
	Endpoint (Population)	Intercurrent Event Strategy ¹	Population Level Summary ¹ (Analysis)	
Supplementary and Sensitivity	
 CFB in mean SNOT-22 (severe CRSwNP patients with asthma) 	
 Included in analysis regardless of treatment discontinuation or SCS use for CRSwNP; WP after surgery for CRSwNP⁴ Disc of treatment assumed based on DRMI³ Remained adherent to treatment without surgery or SCS use for CRSwNP⁵ (effectiveness) Included in analysis regardless of treatment discontinuation, surgery or SCS use for CRSwNP⁶ (treatment policy) 	
 Mean difference between interventions at Week 56² (LSMD from CFB ANCOVA following hybrid WP and MI) 	Appendix 8.2
			
 Mean difference between interventions at Week 56² (LSMD from CFB ANCOVA following hybrid WP/WOCF and DRMI) 	Appendix 8.3
			
 Mean difference between interventions at Week 56² (LSMD from CFB repeated measures ANCOVA) 	Appendix 8.4
			
 Mean difference between interventions at Week 56² (LSMD from CFB repeated measures ANCOVA) 	Appendix 8.5
Safety Objective: To evaluate the safety and tolerability of benralizumab				
Safety	
 Presence of AEs and SAE (all severe CRSwNP patients regardless of co-morbid asthma status) 	Included in analysis regardless of treatment discontinuation ⁶ (treatment policy)	Categorical descriptive	Section 4.2.10.1

PFAS = Primary Full Analysis Set; MCP = Multiple comparisons procedure; CRSwNP = Chronic rhinosinusitis with nasal polyps; SCS = Systemic Corticosteroids; NPS = Nasal Polyps Score; NBS = Nasal Blockage Score; DSS = Difficulty with Sense of Smell; WP = Worst Possible; WOCF = Worst Observation Carried Forward; MI = Multiple Imputation; LSMD = Least Squares Mean Difference; CFB = Change from baseline; ANCOVA = Analysis of Covariance; AE = Adverse event; OLE = Open-label Analysis Set; EoDB = End of treatment during double-blind period; IPD = Investigational product discontinuation; LMS = Lund-Mackay score; SNOT-22 = SinoNasal Outcome Test, 22 item.

¹ All estimand attributes explicitly identified for primary and key secondary endpoints only.

² Week 56 is the multiplicity protected timepoint for co-primary and key secondary endpoints.

³ Treatment Condition: Treatment with benralizumab versus placebo, regardless of compliance, where rescue with surgery and/or SCS use for CRSwNP indicates treatment failure.

⁴ Treatment Condition: Treatment with benralizumab versus placebo, regardless of compliance, where rescue with surgery for CRSwNP indicates treatment failure.

⁵ Treatment Condition: Treatment with benralizumab versus placebo, while on treatment and without rescue by surgery and/or SCS use for CRSwNP.

⁶ Treatment Condition: Treatment with benralizumab versus placebo, regardless of compliance or occurrence of rescue by surgery and/or SCS use for CRSwNP.
